0. SUMMARY

Title	Effect of dapagliflozin on nighttime blood pressure in type 2 diabetes
Protocol number	DAPA-ESR-16-12460
EudraCT number	2017-002125-38
Promotor	LM Diagnósticos S.L. [name]
Principal	[name]
Investigator	Unidad de Hipertensión, Hospital Universitario 12 de Octubre, Madrid.
Coordinator	[name] Grupo de Hipertensión Arterial y Riesgo Cardiovascular, Hospital Universitario 12 de Octubre.
Project office	ODDS SL
[CRO]:	[name]
Centres	Three university hospitals and the primary care centres in their area in Madrid (Clínico San Carlos, La Paz, 12 de Octubre)
Type of study	Randomized, multicentric, placebo-controlled, single-blind pilot study
Main outcome	Nighttime blood pressure in type 2 diabetic patients
Objective	To investigate the effect of the addition of 10 mg daily of dapagliflozin to the treatment of diabetic patients compared to the addition of placebo on the change in nighttime blood pressure (measured by ABPM) over 12 weeks among patients with albuminuria levels \geq 30 and $<$ 3000 mg/g creatinine and estimated glomerular filtration rate \geq 60 mL/min/1.73 m ² ..

Patients	225 patients with a previous diagnosis of type 2 diabetes and eGFR>30mL/min x1,73m ² , office BP above 140/70 mmHg, HbA1C 7.5-10%, albuminuria levels between 30 mg/g creatinine and 3000 mg/g creatinine and estimated glomerular filtration rate \geq 60 mL/min/1.73 m ² .
Intervention	10 mg once daily of dapagliflozin or placebo resembling dapagliflozin.
Chronogram	Administrative issues: 3 months (September-November2018) AEMPS/Ethical committee approval to first subject in: 1 month First subject in: December2018 50% enrollment: April 2019 Last subject in: June 2019 Last subject last visit: September2019 Recruitment of patients: 7 months (December2018-June 2019) Data cleaning and closing of the database: 3 months (october2019-December2019) Data analysis: 4 months (January 2020- April 2020) Final report and drafting of the manuscript: May 2020

1. INTRODUCTION

Cardiovascular (CV) disease is the leading cause of death worldwide, accounting for 30% of all deaths(1). High blood pressure (BP) is the most important individual factor contributing to global burden of disease worldwide (2), and as a consequence BP is the most important modifiable risk factor for CV disease. Prospective cohort studies have established a graded positive association between BP and the risk of CV disease, starting at 115 mmHg for systolic BP measured in the morning(3). The effectiveness of antihypertensive therapy was initially demonstrated in patients with systolic BP above 160 mmHg and the results of early prospective trials were reviewed two decades ago(4). More recently, the possibility of measuring BP out of the office has opened the investigation about the caveats of office BP measurements mainly consisting of white coat hypertension, masked hypertension, short-term BP variability, and nighttime BP, all these situations are characterized by an increase in CV and renal risk when compared to well controlled arterial hypertension(5, 6). The most relevant differences according to the accompanying risks is the one observed when daytime and nighttime BP levels are compared. Nighttime BP has shown to be the one accompanied by the highest level of risk when it is elevated(5). Data from the Spanish ABPM Registry(7) have shown that nighttime BP in albuminuric type 2 diabetics shows a significant difference when compared to values obtained in non-albuminuric type 2 diabetics. The same is true in non-diabetic patients with higher nighttime BP levels when albuminuria is present albeit not as much as in type 2 diabetics (7). According to our data, the differences in nighttime BP oscillates on average between 9-12 mmHg (7). Such a difference can account for the development of albuminuria as shown by Lurbe et al. type 1 diabetics(8). Both albuminuria and elevated nighttime BP are significant predictors of cardiovascular (CV) events and

deaths as well as of progression of chronic kidney disease (CKD)(5, 9), hence the control of nighttime BP could translate into a better CV protection and in a significant diminution of albuminuria if present.

The newest class of drugs for type 2 are the sodium glucose co-transporter 2 receptor (SGLT-2) inhibitors. These reduce the reabsorption of renal-filtered glucose back into the bloodstream, thereby leading to loss glucose in the urine. The Figure 1 obtained from Rajasekeran et al. (10) shows the main mechanisms of action of these drugs mediated mainly through glycosuria and natriuresis.

[figure not shown]

Figure 1. Cardiorenal protection of SGLT2 inhibitors mediated by glycosuria and natriuresis. Obtained from Rajasekeran et al.(10)

Other protective effect directly related to the heart improving left ventricular function and diminishing left ventricular mass have been described for these drugs(11, 12). Recently, the Empagliflozin Cardiovascular Outcome and Mortality in Type 2 Diabetes (EMPA-REG) trial(13) demonstrated the capacity of empagliflozin to significantly reduce the relative risk for both CV mortality and all-cause mortality as well as hospitalizations due to heart failure in type 2 diabetic patients. The study also demonstrated the capacity of the drug to slow the progression of kidney disease in type 2 diabetic patients together with the finding of a significantly lower risk of clinically relevant renal events(14).

SGLT2 antagonists are drugs with the capacity to lower BP above the level obtained by commonly used antihypertensive drugs(15).The decrease in BP contributes importantly to the good effects observed in EMPA-REG study(13).Dapagliflozin also improves significantly BP and does it during 24 hours(16).

We have hypothesized that the capacity of dapagliflozin to lower BP could be particularly intense during nighttime. This in turn could participate in the observed decay in albuminuria. Should this hypothesis be confirmed, it could contribute importantly to the potential positive influence of all SGLT2 in preventing mortality and hospitalization due to heart failure as shown by the EMPA-REG study(13).

2. OBJECTIVES

Primary Objective:

To investigate the effect of the addition of 10 mg daily of dapagliflozin to the treatment of diabetic patients compared to the addition of placebo on the change in nighttime blood pressure (measured by ABPM) over 12 weeks among patients with albuminuria levels ≥ 30 and < 3000 mg/g creatinine and estimated glomerular filtration rate ≥ 60 mL/min/1.73 m².

Secondary objectives:

- 1) To investigate the effect of the addition of 10 mg daily of dapagliflozin to the treatment of diabetic patients compared to the addition of placebo on the change in nighttime blood pressure (measured by ABPM) over 12 weeks in the subgroup of patients with high (30-300 mg/g creatinine) albuminuria levels.
- 2) To investigate the effect of the addition of 10 mg daily of dapagliflozin to the treatment of diabetic patients compared to the addition of placebo on the change in nighttime blood pressure (measured by ABPM) over 12 weeks in the subgroup of patients with very high (>300 mg/g creatinine) albuminuria levels.
- 3) Changes in albuminuria, office BP and HbA1C in the two subgroups of patients investigated

3. METHODS

This clinical trial will be conducted according to this Protocol, under the Regulation (EU) No 536/2014 and all regulatory requirements applicable to clinical trials and following the principles of Good Clinical Practice.

3.1. STUDY DESIGN

Type of study: Randomized, multicentric, placebo-controlled, single-blind pilot study.

3.2. PATIENTS

Type 2 diabetic patients recruited in the primary care setting in the area of three university hospitals in Madrid, irrespectively of the time since diagnosis and type of treatment received for their diabetes.

Entry criteria

- Patients with a previous diagnosis of type 2 diabetes and
 - Estimated glomerular filtration rate (eGFR) $\geq 60 \text{ mL/min} \times 1.73\text{m}^2$ and
 - Diagnosis of essential hypertension established at least one year before inclusion visit and suboptimal BP control (office BP above 140/70 mmHg)
 - HbA1C 7.5-10%
 - Albuminuria levels $\geq 30 \text{ mg/g}$ of creatinine

Exclusion criteria

- Age < 18 years old or ≥ 75 years old.
- Women of childbearing potential. A woman is considered of childbearing potential (WOCBP), i.e. fertile, following menarche and until becoming post-menopausal unless permanently sterile. Permanent sterilisation methods include hysterectomy, bilateral

salpingectomy and bilateral oophorectomy. A postmenopausal state is defined as no menses for 12 months without an alternative medical cause.

- Type 1 diabetes
- Albuminuria above 3000 mg/g of creatinine
- Established cardiovascular disease (stable heart failure, peripheral arterial disease or myocardial infarction or stroke within the previous 6 months)
- Intolerance to dapagliflozin
- On treatment with loop diuretic
- On treatment with SGLT2 inhibitors.
- On treatment with pioglitazone.
- Patients diagnosed of hereditary problems of galactose intolerance, Lapp lactase deficiency or glucose-galactose malabsorption.
- Patients who routinely work during nighttime (period between 11.00 p.m. and 7.00 a.m.)

3.3. DESCRIPTION OF THE INTERVENTION

The drug under evaluation, dapagliflozin, is approved to be used in adults who are 18 or older with type 2 diabetes mellitus for improving glycemic control and can be used in monotherapy when diet and exercise alone do not achieve good glycemic control and metformin use is not indicated due to intolerance, or in combination with other hypoglycemic agents, including insulin, when these, added to diet and exercise do not achieve good glycemic control. In this study it will be used in agreement with the terms in which its use is authorized.

The participants in the study, in addition to the treatment for their diabetes that were receiving from their attending physician, will receive 10 mg once daily of dapagliflozin or placebo resembling dapagliflozin. The randomization scheme follows below.

[figure not shown]
3.4. RANDOMIZATION

Two strata will be considered based on albuminuria levels:

- High albuminuria (30-300 mg/g creatinine)
- Very high (>300 mg/g creatinine)

Patients will be randomized to either dapagliflozin or placebo in a 2:1 ratio.

Figura 2.-Randomization scheme

Total number of patients: 225; distributed as:

- 150 diabetic patients treated with dapagliflozin (10mg/day in a single dose), half of them with high albuminuria levels (albuminuria 30-300 mg/g of creatinine) and half with very high albuminuria levels (albuminuria > 300 mg/g of creatinine)

- 75 diabetic patients treated with placebo, half of them with high albuminuria levels (albuminuria 30-300 mg/g of creatinine) and half with very high albuminuria levels (albuminuria > 300 mg/g of creatinine)

Randomization will be stratified by albuminuria strata and participating hospital (three hospitals); center specific randomization lists (active treatment or placebo) will be prepared centrally at the project office with a treatment code assigned to each patient.

Allocation will be concealed by means of sequentially numbered, opaque, sealed envelopes that contain the medication code assigned. The envelopes have to be opened sequentially and only after the participant's name is written on the appropriate envelope.

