3.11. SAMPLE SIZE CONSIDERATIONS

For the main objective of the study, changes in mean nocturnal systolic blood pressure will be compared between the active treatment and placebo groups.

The use of SGLT2 inhibitors has been reported to be associated with reductions in office blood pressure of 4–8 mmHg, reductions that could be even higher with the use of ambulatory BP monitoring.¹⁵

Accepting an alpha error of 0.05 in a two-sided test, 150 patients are needed in the active treatment group and 75 in the placebo group (2:1 randomization) to have an 80% power (beta error=0.2) to detect as statistically significant a difference greater than or equal to 5 mmHg in mean nocturnal BP between placebo and active treatment (conservative estimate of the expected effect). The standard deviation is assumed to be 12 mmHg and it is expected a drop-out rate of 9%.

In the prespecified subgroup analysis by albuminuria levels, this sample size (75 in active treatment and 37 in placebo) allows to detect as statistically significant, within each albuminuria stratum and with the same assumptions and alfa and beta errors, a difference greater than or equal to 7,1 mmHg in the reduction of mean nocturnal BP between both groups (active treatment and placebo), an effect still within what can be expected.

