3.13. PLAN OF ANALYSIS

The main analysis will compare baseline and final visit values of nocturnal blood pressure and all the rest of quantitative variables of interest within each stratum of albuminuria by means of paired t-test. Changes of nighttime blood pressure from baseline to final visit among patients with high and very high albuminuria levels will be compared to placebo with t-test.

Variables will be described by means of mean (and standard deviation) or proportion depending on the type of variable considered. Whenever the test of hypothesis may involve discrete variables, chi-squared test will be used.

Comparability of treatment and placebo groups will be tested (t-student or chi-squared test, depending on the variable) to assess randomization, and linear regression will be used to adjust for potential confounders, if needed; stratum of albuminuria at randomization will be forced in the model.

To respond to secondary objectives, the same analyses will be done for each stratum of albuminuria at randomization.

Only patients that complete the 3-month follow-up will be analyzed. Patients who do not complete the follow-up will be compared to those who adhere to the protocol.

No interim analysis is planned. A *p* value<0.05 will be considered as statistically significant.

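### Randomisation is stratified by albuminuria and hospital, but the between-arm t-test ignores both and hospital appears in no analysis, so precision is lost if hospitals differ in BP change.

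*Combined protocol and SAP*

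**What the plan says.** Protocol section 3.4 (Randomization) names two design factors: "Randomization will be stratified by albuminuria strata and participating hospital (three hospitals"). That gives 2 x 3 = 6 cells, with a separate list for each centre. The allocation is 2:1: "Patients will be randomized to either dapagliflozin or placebo in a 2:1 ratio". The section does not say whether the lists are blocked.

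Section 3.13 (Plan of analysis) is the only analysis section. It tests change within arm by paired t-test and change against placebo by two-sample t-test. Linear regression comes in only where adjustment for confounders is judged necessary, after a comparison of the arms at baseline. For that regression, "stratum of albuminuria at randomization will be forced in the model". Hospital is named in no analysis, and the analyses for the secondary objectives repeat the same methods within each albuminuria stratum.

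The precision that was planned for is in section 3.11: "Accepting an alpha error of 0.05 in a two-sided test", sized "to have an 80% power (beta error=0.2") for "a difference greater than or equal to 5 mmHg in mean nocturnal BP between placebo and active treatment". It adds "The standard deviation is assumed to be 12 mmHg" and "it is expected a drop-out rate of 9"%.

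**The concern.** If randomisation forces the arms to be balanced within hospital, differences between hospitals in BP change cannot contribute to the sampling error of the treatment difference. An analysis that omits hospital still leaves those differences in the residual variance. The standard error it reports is then larger than the true one, and the p-value is too large.

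The plan accepts the principle for one stratification factor and does not carry it to the other. The regression clause does not repair this. It is triggered by imbalance at baseline, and stratification is there to prevent imbalance by hospital, so such a check will tend not to select it. The reason to include hospital is precision, not confounding.

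At stake is some power in a trial with no reserve beyond 80%, and in stratum analyses that are sized only for 7.1 mmHg. A choice of model would also be left open until after the data are seen, by a team whose investigators hold the treatment codes (section 3.5).

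**Working it through.** **Inputs from the protocol.** Two-sided alpha 0.05, power 80%, difference 5 mmHg, SD 12 mmHg, drop-out 9% (section 3.11); 2:1 allocation, two albuminuria strata, three hospitals (section 3.4); completers only (section 3.13).

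**Input not in the protocol.** The between-hospital SD of the *change* in nocturnal BP, written s. Values of 2, 3, 4 and 5 mmHg are assumed, with the total SD held at 12. They correspond to s²/144 = 2.8%, 6.3%, 11.1% and 17.4% of the variance.

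**1. The plan's own figures.**
- Placebo n = (1 + 1/2) x 12² x (1.960 + 0.842)² / 5² = 67.8, so 68; active 136.
- With 9% drop-out: 68/0.91 = 74.7, so 75; 136/0.91 = 149.5, so 150. The total of 225 is reproduced.
- Within a stratum: 12 x (1.960 + 0.842) x √(1/34 + 1/68) = 7.06 mmHg, or 7.08 with unrounded completers (33.67 and 68.25). The stated 7.1 is reproduced.

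**2. Standard error without hospital.** 12 x √(1/68 + 1/136) = 1.782 mmHg.

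**3. Standard error with hospital.** 1.782 x √(1 − s²/144). If the lists are balanced within hospital, this is also the true sampling error of the analysis that omits hospital. In that case:
- type I error without hospital = 2 x [1 − Φ(1.96 / √(1 − s²/144))];
- power without hospital = Φ((5 − 1.96 x 1.782) / SE with hospital);
- power with hospital = Φ(5 / SE with hospital − 1.96).

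| s (mmHg, assumed) | SE with hospital | Type I error, hospital omitted | Power at 5 mmHg, omitted | Power at 5 mmHg, included |
|---|---|---|---|---|
| 0 | 1.782 | 5.0% | 80.1% | 80.1% |
| 2 | 1.757 | 4.7% | 80.4% | 81.2% |
| 3 | 1.726 | 4.3% | 80.9% | 82.6% |
| 4 | 1.680 | 3.8% | 81.5% | 84.5% |
| 5 | 1.620 | 3.1% | 82.4% | 87.0% |

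The gains in power are 0.8, 1.7, 3.0 and 4.6 points. At smaller shares of variance, 1% and 2%, the standard error with hospital is 1.773 and 1.764, so the one without is 0.5% and 1.0% too large. Power with hospital is then 80.5% and 80.9%.

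**4. Dependence on blocking.** Simulation used 204 completers, six equal cells, 4,000 runs per setting, and hospitals explaining 10% of the variance.
- Blocks of 3 (assumed): the albuminuria-only model reports a mean SE of about 1.78, while the actual SD of the estimate is 1.683 to 1.722. With hospital the mean reported SE is about 1.69. Power is 81.9% without hospital and 85.2% with it.
- No blocks: the albuminuria-only model reports 1.791 against an actual SD of 1.793 to 1.824, so it is about valid. With hospital the reported SE is about 1.707. Power is 80.3% and 83.4%.
- No hospital differences, with blocks: power is 79.7% without hospital and 79.6% with it.

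In the blocked null runs, rejection was 4.6% without hospital (closed form 3.9%) and 5.7% with it (nominal 5%). The Monte Carlo error is about 0.3 points and both rates came out high in the same runs, so the closed-form values are the ones to rely on.

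**The case against.** **The overstated standard error needs an unstated fact.** It follows only if the lists are balanced within strata, for example by permuted blocks, and section 3.4 does not say so. This stands. A reader might infer that stratification alone makes the reported standard error wrong once hospitals differ. The documents do not support that; without blocking, only precision is lost.

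**Hospital differences in change are not established.** A reader might infer them from local measurement. But section 3.9 names one device and a fixed clock window, both ABPM recordings are made at the hospital (section 3.20), and a constant offset at a hospital cancels in a change score. Local laboratory handling bears on albuminuria and HbA1c, not on nocturnal BP. This stands too: the range of 2 to 5 mmHg is an assumption and may lean high.

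**The consequence is small and on the safe side.** There is no bias and no excess of false positives. Under the assumptions used, power with hospital omitted stays at 80% or above. Section 3.13 plans no confidence intervals, so wide intervals are not a planned output that can be criticised.

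**Regression for confounders could admit hospital.** It could, but only at discretion, and it would leave the t-test as it is. This does not close the gap.

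**Conclusion.** The mismatch between sections 3.4 and 3.13 is real, and it is wider for the t-test, which drops both design factors when pooled, than for the regression, which drops one. The size is modest. For an assumed between-hospital SD of change of 2 to 5 mmHg, the standard error falls from 1.782 to between 1.757 and 1.620 when hospital is included, and power at 5 mmHg rises by about 1 to 5 points. Type I error of 4.7% to 3.1% applies only if the lists are balanced within strata. If hospitals do not differ in BP change, essentially nothing is gained or lost.

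A reader might infer that the trial's error control or its sample size is compromised. Neither follows: any error is conservative, and the 225 is reproduced from an SD of 12 with no adjustment assumed. The change is worth making because it is nearly free and because adding hospital after the data are seen would look data-driven.

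**What to change.** In section 3.13, replace the between-arm t-test with a linear model of change from baseline on treatment, albuminuria stratum and hospital, as fixed terms. Within an albuminuria stratum, use treatment and hospital. Specify this for the primary endpoint and the secondary quantitative endpoints (office BP, HbA1c, albuminuria), and remove the condition that makes the regression discretionary. Editing the regression clause alone would leave the primary comparison unchanged. In section 3.4, state whether the lists are blocked, without giving sites the block size.

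Cost: a few lines of text. Hospital takes two degrees of freedom out of about 200, and albuminuria takes one more relative to the plain t-test. No new data are needed, since the lists are already specific to each centre, and the sample size does not change.

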3.5. DRUG UNDER EVALUATION. BLINDING AND RELABELLING OF THE MEDICATION

The investigational medicinal product (IMP) is dapagliflozin 10 mg given once daily (film coated tablets, oral use).

The comparator will be placebo matching dapagliflozin 10 mg.

Either dapagliflozin or placebo will be administered through out the planned intervention period of the study (12 weeks).

AstraZeneca will donate both dapagliflozin 10 mg and placebo resembling dapagliflozin 10 mg for the study.

Identity of investigational product(s)

Investigational product	Dosage form and strength	Manufacturer
Dapagliflozin	10 mg, Green, plain, diamond shaped, film coated tablet (orally)	AstraZeneca
Matching placebo for dapagliflozin	Green, plain, diamond shaped, film coated tablet (orally). Does not contain active ingredient	AstraZeneca

Primary packaging of the Investigational Medicinal product (IMP) will be carried out by AstraZeneca or their designee in accordance with Good Manufacturing Practice (GMP).

Unlabeled bottles (identical) containing 35 tablets of each IMP will be provided by AstraZeneca.

The tablets contain lactose, which may cause discomfort in lactose-intolerant individuals.

Label, storage and distribution are a promotor's responsibility.

Preparation and labelling of Investigational Medicinal Product

To allow for adequate treatment for the diabetes, only participants will be blinded to the treatment they receive. Attending physicians will know the group in which every patient is. To preserve blinding for the patient, the study medication (active and placebo) will be sent from AstraZeneca to a certified company (LogistaPharma), where, in coordination with the CRO of the study [ODDS, S.L.], it will be counted, labeled and distributed to the participating centers. The IMPs will be labelled in accordance with Good Manufacturing Practice (GMP) and local regulatory guidelines for labeling. The labels will fulfill GMP Annex 13 requirements for labelling.

LogistaPharma will send labeled medication with the corresponding randomization codified list to Hospital 12 de Octubre (Pharmacy Service). The investigator coordinator of the trial will distribute the medication **to** the primary care investigators. The study is single blinded, every investigator in each of the sites will have the randomization list with the individual treatment codes for each individual patient. The unblinding for the patient must not be done unless in medical emergencies. If the codes are broken for an individual patient, the promotor must be notified and decision if the data should be excluded from the analysis must be done by the promotor

The patient will receive the labelled medication, and counting of the pills will be done in the following visits: week 4, week 8 and week 12. Patients will also receive the medication leaflet of dapagliflozin, as stated in the form "Information for the patient"

Storage

All study drugs will be kept in a secure place under appropriate storage conditions. The IMP label on the bottle specifies the appropriate storage.

At the end of the study, all the study medication that has not been used will be collected from the patients by the investigators to be properly destroyed.

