3.9. VISITS, VARIABLES AND MEASUREMENTS

Four clinical visits are planned in every patient at 0 (recruitment and randomization), 4, 8 and 12 weeks. Information on personal and family history of disease, clinical examination (including office BP determination), ABPM and blood and urine samples will be obtained on visits 0. The variables measured in the blood and urine samples depend on the criterium of the attending physician. For this trial, only HbA1c, serum creatinine, estimated glomerular filtration rate (eGFR) and albuminuria are mandatory. All this information, except personal and family history of disease, will also be collected at week 12 (see “3.20. Conduct of the study”). Thirty days after the end of the medication (visit of week 12) all participants will be contacted by telephone to assess safety. For the initial laboratory data required in the CRF, data obtained in primary care in the previous 3 months could be valid. These data will be repeated at the end of the study. Informed consents for the study will be signed by the patients before coming to the hospital. Blood samples extractions included in this protocol will be done, handled and analyzed at each clinical setting according to usual clinical

practice. No blood sample storage will be needed in this study. Extra blood samples drawn will be handled as described in “3.23. Addendum”.

The relationship of the procedures performed at every clinical visit is presented below (see “3.20. Conduct of the study”). Case report forms (CRFs) are presented in Annex I. Albuminuria will be measured according to generally used and previously described methodologies(18-23).

ABPM will be measured using Mobil-o-Graph that will give us 24 hours brachial and central BP as well as pulse wave velocity and heart rate(24). As diary of activity of the patient will not be recorded, in this study, nocturnal (or nighttime) blood pressure refers to measurements within the period from 12.00 p.m. to 6.00 a.m.

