3.10. WITHDRAWAL OF PATIENTS FROM THE STUDY AND UNBLINDING

Any patient can be withdrawn from the study at anytime during follow-up based on medical criteria of attending physician. The latter will detail the reasons of the withdrawal and communicate it urgently to the coordinating office of the trial if needed. If the reason for withdrawal is an adverse event (AE), the patient will be followed according to the procedures described for AEs (3.16).

Any patient can decide to abandon the study at any time during the study.

Withdrawal from the trial for any reason is definitive. When leaving the study, the main reason will be recorded and, if possible, the patient should have a final exam with the content of the visit of week 12. Patients that abandon the study will not be substituted.

All the above mentioned situations cause unblinding of the study. The primary care physician is always aware of the medication that receives the patient (single blind) and

will be the contact person and responsible to break the blind. Contact details are available in the patient information form. After unblinding, the responsible primary care physician will report it to the coordinating office of the project (ODDS, S.L., [contact]).

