3.12. DATA MANAGEMENT

Data will be collected in an electronic CRF by participating doctors and nurses both at the hypertension units and at primary care centers. A range of acceptable values and logical rules among variables will be implemented to improve quality of data and reduce the need of queries.

The processing, communication and transfer of data will be in accordance with the provisions of the Organic Law 15/1999, December 13th, on the protection of personal data.

Trial documentation will be kept and storaged in each site for 25 years after completion of the study.

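### Section 3.5 gives the randomization list to all investigators, wider than its own reason for single-blinding, leaving week-12 assessors unmasked and the next assignment foreseeable

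*Combined protocol and SAP*

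**What the plan says.** **Who is blinded, and why.** Section 3.5 states: "To allow for adequate treatment for the diabetes, only participants will be blinded to the treatment they receive". The next sentence identifies who is meant to know: "Attending physicians will know the group in which every patient is". Section 3.10 opens a sentence with "The primary care physician is always aware of the medication that receives the patient (single blind) and" and ends it by making that physician responsible for breaking the blind.

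**Who receives the list.** Section 3.5 goes further: "every investigator in each of the sites will have the randomization list with the individual treatment codes for each individual patient". The lists are not neutral codes, since 3.4 says that "center specific randomization lists (active treatment or placebo) will be prepared centrally at the project office with a treatment code assigned to each patient".

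**How allocation is concealed.** Section 3.4 relies on "sequentially numbered, opaque, sealed envelopes that contain the medication code assigned", opened in order and only once the participant's name is on the envelope.

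**Who measures.** The visit table in 3.20 places baseline office BP in primary care. It places randomisation, both ABPM recordings and the week-12 office BP at the hospital. Section 3.9 says of the baseline set, which includes office BP and ABPM, "All this information, except personal and family history of disease, will also be collected at week 12". Section 3.12 adds: "Data will be collected in an electronic CRF by participating doctors and nurses both at the hypertension units and at primary care centers".

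No section provides for a masked outcome assessor or a masked statistician.

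**The concern.** The stated reason for unblinding is a treatment need, and it belongs to the physician managing the diabetes. It gives no ground for the hospital team to know the arm, nor for anyone to know it before the patient is randomised. Two things are at stake.

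1. **Outcome assessment.** Change in office BP from week 0 to week 12 is a secondary endpoint in 3.8. The final reading is taken at the hospital after randomisation, and nothing keeps the arm from whoever takes it. Knowledge of the arm can influence an observer-taken reading.
2. **Allocation concealment.** A sealed envelope conceals only if nobody involved in enrolment already knows what it contains. If investigators hold a list linking codes to active or placebo, in an order matching the envelopes, the envelope hides nothing from them. Deciding whom to enrol, or when, with that knowledge could unbalance the arms at baseline. Such an imbalance would bear on every endpoint, including the device-recorded one.

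**Working it through.** **Step 1. Does the access match the reason?**

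| Question | What the plan says | Section |
|---|---|---|
| Why is anyone but the patient unblinded? | To treat the diabetes adequately | 3.5 |
| Whom does that reason cover? | Attending physicians; the primary care physician | 3.5, 3.10 |
| Who gets the list? | All investigators at all sites | 3.5 |
| What does the list show? | Active or placebo, with a code per patient | 3.4 |
| Who takes week-12 office BP and fits the ABPM? | The hospital | 3.20 |
| Who breaks the blind? | The primary care physician | 3.10 |

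Access is wider than the reason. Neither the reason for unblinding nor the unblinding procedure requires hospital assessors to hold the list.

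**Step 2. Does the concealment hold?** Section 3.4 puts a code in the envelope. Section 3.5 gives investigators the key to the codes. The plan neither says when they receive it nor withholds it until a patient is randomised. Read together, the two sections let a list-holder who knows the place in the sequence foresee the next arm.

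**Step 3. Which endpoints are exposed to the assessor?**
- Nocturnal BP (primary, 3.8) comes from the Mobil-o-Graph over a fixed clock window (3.9). The assessor neither reads the value nor chooses the night period. Direct exposure is likely small.
- Office BP (secondary, 3.8) is taken by staff at the visit. It is the exposed measurement.

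**Step 4. The plan's own sample size.** Inputs from 3.11: difference 5 mmHg, SD 12 mmHg, two-sided alpha 0.05, power 80%, allocation 2:1, drop-out 9%.

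n(placebo) = (1.960 + 0.842)² × 12² × (1 + 1/2) / 5² = 67.8, so 68; n(active) = 136.

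After drop-out: 68/0.91 = 74.7, so 75; 136/0.91 = 149.5, so 150. The total of 225 is reproduced. Masking assessors changes none of these figures.

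**Step 5. Illustration of an office-BP bias.** The documents give no size for assessor bias, so the shifts below are assumptions. Against the 4–8 mmHg office-BP reduction quoted in 3.11:
- 1 mmHg is 1/8 = 13% to 1/4 = 25%.
- 2 mmHg is 2/8 = 25% to 2/4 = 50%.

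For the effect on false positives, also assume that the 12 mmHg SD given for nocturnal BP applies to change in office BP, with 68 and 136 completers:

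SE = 12 × √(1/68 + 1/136) = 1.78 mmHg.

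Two-sided type I error with a spurious difference b = Φ(b/SE − 1.96) + Φ(−b/SE − 1.96).

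| Assumed b (mmHg) | Type I error, office BP |
|---|---|
| 0 | 5.0% |
| 0.5 | 5.9% |
| 1 | 8.7% |
| 2 | 20.2% |
| 3 | 39.1% |

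The table shows how sensitive the test is to a small systematic shift. It does not estimate the shift.

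**The case against.** Single-blinding is declared openly in a pilot study with a reason attached, and the primary endpoint is recorded by a device. Nor do the documents say that the person measuring at week 12 holds the list. The sentence on list access follows one about primary care investigators, and 3.10 names only the primary care physician as always aware. A hospital nurse who is not an investigator might never see it.

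Much of this stands. That hospital assessors know the arm is an inference from two statements: that only participants are blinded, and that all investigators at all sites have the list. What the text does establish is that nothing masks them. The timing of list delivery is also unstated, so foreknowledge is a possibility the plan leaves open. A primary care recruiter would also need to know the current place in the hospital's list.

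A reader might infer more than the documents support:
- *That the primary result is compromised by unmasked assessors.* The device and fixed window in 3.9 argue against a large direct effect.
- *That unblinded staff will decide which ABPM recordings to repeat or reject.* No section describes such decisions or who makes them.
- *That subgroups could be chosen knowing the arm.* The albuminuria strata are fixed in section 2, 3.4, 3.11 and 3.13.
- *That restricting the list would mask exclusions after a code break.* Section 3.5 gives that decision to the promotor, whom this change does not affect.
- *That hospital staff could be fully masked.* A hospital pharmacy receives the coded list (3.5) and the project office prepares the lists (3.4). Urine samples and adverse-event monitoring at week 12 (3.20) may also hint at the arm.
- *That the trial ought to be double-blind.* That is a separate trade-off, not argued here.

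**Conclusion.** The point holds in limited form. Section 3.5 distributes the list more widely than its own reason for single-blinding supports. Two consequences follow from the text: week-12 office BP is measured with no provision for masking, and the concealment in 3.4 fails for any investigator who has the list before the patient is randomised.

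The size of any bias cannot be derived from the documents. The 13–50% range rests on an assumed shift of 1–2 mmHg; the type I error of 8.7–20.2% for the same shift also assumes an office-BP SD of 12 mmHg. Direct assessor bias in nocturnal BP is likely small. Any selection through foreseen assignments would not be limited to office BP, but the documents offer no basis for quantifying it. The change is worth making because it is cheap and leaves the attending physician's knowledge of the treatment as planned.

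**What to change.** Amend 3.5, and align 3.4 and 3.10 with it, so that:
1. No investigator holds the randomization list before a patient is randomised.
2. After randomisation, that patient's treatment code is released only to that patient's attending (primary care) physician.
3. Hospital staff who measure office BP and ABPM at week 12 have no access to the list or to released codes.
4. The statistician has no access until database lock.

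Matching tablets, identical bottles, coded envelopes and the split of visits between primary care and hospital already support this. The unblinding route through the primary care physician stays as it is.

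The cost is a small handling effort for per-patient release. That hospital and primary care staff are different people is inferred from visit locations, so each site should confirm it; the same applies to the statistician and the list-preparing office.

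Masking may remain incomplete for the reasons given above. The change also does not remove bias from medication changes made by unblinded attending physicians; under 3.6, changes that do not lead to withdrawal are only recorded.
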